11.2.2. Control of Systematic Error/Bias

Selection of subjects will be made from the investigator's population. All subjects that have signed the ICF will be enrolled in the study.

11.2.3. Number of Subjects per Investigative Site

To avoid any center effect and bias, individual centers will not be allowed to enroll more than 20 subjects meeting enrollment criteria, unless Boston Scientific gives written approval to do so. Enrollment of an amount of study subjects in excess of such approved number of 20 total subjects must first be approved by sponsor, notified/submitted to Institution's IRB/EC, as applicable, and requires an amendment of exhibit A of the clinical study agreement.

11.3 Data Analyses

11.3.1. Interim Analyses

No formal interim analyses are planned for the purpose of stopping the study early for declaring effectiveness or for futility. Analysis of each endpoint will be performed when all applicable data for that endpoint has been collected. Analyses of acute data (procedural safety and acute procedural success) may be performed and used for publication purposes after completion of study enrollment, index procedure, 7 day and 3 month follow-up of all subjects.

11.3.2. Subgroup Analyses

Additional ancillary analyses on specific subgroup of subjects, may be presented.

These analyses will include but not limited to the following:

- Age (< 60 versus \geq 60 years);
- Gender (Male versus Female);
- Monitoring (Subjects with data from continuous ECG recording systems (eg. ILR, PM, ICD, CRT) versus those without).

11.3.3. Justification of Pooling

Center-to-center heterogeneity will be assessed for the primary endpoints by performing a random effects logistic regression analysis. Centers with less than five enrollments will be combined to form "supercenters". Small centers will be combined until the newly created supercenter has five enrollments, and then a new supercenter will be created. Centers will be

deemed to be heterogeneous if the variance of the random center effect is found to significantly differ from zero. A significance level of 15% will be used for this test.

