7.3. Justification for the Study Design

According to the most recent guidelines, catheter ablation has deemed effective in restoring and maintaining sinus rhythm and reducing symptoms in subjects with symptomatic recurrent AF. The main goal of the study is to demonstrate the procedural success under real world conditions and document safety in a post market setting.

POLAR SMART is a prospective, multicenter, single arm, post-market study to collect real-world clinical data on safety, effectiveness and procedural success of Boston Scientific Cardiac Cryoablation System (POLARx™ System) when use to perform PVI in the ablation treatment of De Novo AF.

The study is intended for collecting data in South Korea and Japan. Health care utilization, health economic and ethnic differences may have an impact on therapy in real world settings. PMCF data are helping to understand differences and equalities across patient cohorts from different enrollment regions and may support local guideline adjustments.

The subject population has been chosen based on clinically indication for PVI ablation procedure (in compliance with IFU / Tenpubunryo as legally approved conditions). This study will collect real-world data on acute and chronic safety and effectiveness and extend the follow up to 12 months. In addition, adverse events will be collected through the follow-up period and will be compared to rates from literature

De novo subjects are selected where a cryoballoon will be used for first PVI. To determine the performance of the Cryoablation Balloon Catheter, an analysis of the ability to electrically isolate a targeted PV acutely will be completed. PVI measurements will be taken post cryo application to assess entrance block at the minimum.

In comparison to available alternative systems, the novel POLARx™ showed similar safety and efficacy compared to the Medtronic fourth generation of arctic front cryoballoon (AF-CB4). A higher rate of real-time PV recordings and significantly lower minimal balloon temperatures were observed using the POLARx™ (20).

This study is further contributing to the PMCF data collection, mandated under MDR, on the “POLARx™ Cardiac Cryoablation Catheter System”. This study protocol and procedures have been designed to minimize any study burden for study subjects, including the selection and training of investigators. Patients may benefit from more advanced technology which is especially focused on procedure success and timing.

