This study will also allow to capture roof-line ablations as part of prophylactic treatment in addition to PVI. This additional ablation has increasing importance in Japanese daily clinical routine. It is unknown to what extend these techniques are used and how those are impacting safety and efficacy of Cryoablation based PVI only. This study will allow an increased sample size in order to provide information on changes in clinical practice when PVI Cryoablation is used in combination with roof line ablation.

8. Subject Selection

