Exclusion Criteria	
22. Subject is unable or not willing to complete follow-up visits and examination for the duration of the study;
 
23. Subjects with life expectancy \leq 1 year per investigator's medical judgement;
 
24. Women of childbearing potential who are, or plan to become, pregnant during the time of the study (assessment per investigator's discretion);
 
25. Subjects with unrecovered/unresolved AEs from any previous invasive procedure;
 
26. Subjects who are currently enrolled in another investigational study or registry that would directly interfere with POLAR SMART study. Exception when the subject is participating in a mandatory governmental registry, or a purely observational registry with no associated treatments. Each instance must be brought to the attention of the sponsor for approval.

---------------------------	--

9. Subject Accountability

9.1. *Point of Enrollment*

Investigators will select subjects who are appropriate for study inclusion as per eligibility criteria as specified under section 8.2 and 8.3. Subjects who have given written informed consent are considered enrolled in the study. No protocol-related activities can take place or no data from the subject can be collected until the Informed Consent Form (ICF) is signed and dated by the subject. Screening tests that are part of SOC can be used to determine pre-eligibility. Data from examination performed prior to consent/enrollment (e.g. TTE) will be collected as medical history data after the subject is consented/enrolled in the study. It is the investigator's site responsibility to assess eligibility criteria before obtaining the ICF.

9.2. *Withdrawal*

All subjects enrolled in the clinical study (including those withdrawn from the clinical study) shall be accounted for and documented. If a subject withdraws from the clinical investigation, the reason(s) shall be reported. If such withdrawal is due to problems related to device safety or performance, the investigator shall ask for the subject's permission to follow his/her status/condition as standard of care practice. Withdrawn subjects will not be replaced.

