11.2.1. Analysis Sets

The main analyses for all endpoints will be limited to PVI-only subjects. All available data from these subjects will be utilized. An additional summary of acute primary safety endpoint results (per Section 6.2.1) and adverse events will be provided for all Attempt subjects. Also, additional endpoint analyses may be performed on all Treatment subjects, subjects treated

with a POLARx™ FIT device, as well as subgroups of subjects who did have additional ablations beyond PVI. These subgroups include, but are not limited to:

- Subjects undergoing CTI
- Subjects undergoing CTI and other RA ablations
- Subjects undergoing LA ablations beyond just PVI.

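### The pooling check in 11.3.3 has no country term, so a moderate Japan–South Korea difference would usually go undetected at 200 subjects and could not be attributed to country if a signal appeared

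*Combined protocol and SAP*

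**What the plan says.** About 30 sites in Japan and South Korea contribute to one pooled Kaplan-Meier rate per primary endpoint (sections 7.1 and 11.1.1). On the analysis set, section 11.2.1 states: "The main analyses for all endpoints will be limited to PVI-only subjects".

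The check on pooling is in section 11.3.3: "Center-to-center heterogeneity will be assessed for the primary endpoints by performing a random effects logistic regression analysis". Centers are "deemed to be heterogeneous if the variance of the random center effect is found to significantly differ from zero". The threshold is explicit: "A significance level of 15% will be used for this test". Centers below five enrollments are merged: "Small centers will be combined until the newly created supercenter has five enrollments". Nothing limits merging to centers in the same country.

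Country is not named in 11.3.2 (age, gender, monitoring), in 11.3.4 (demographics, baseline characteristics, procedural techniques) or in 11.3.5. All three lists are worded as open.

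Section 7.3 says that health-care utilization, economic and ethnic differences may influence therapy. It adds that the data help to understand "differences and equalities across patient cohorts from different enrollment regions" and may support local guideline changes. On roof-line ablation it says: "This additional ablation has increasing importance in Japanese daily clinical routine".

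**The concern.** The plan pools two countries whose care it expects may differ, and the only prespecified check on that pooling does not ask about country. A center-variance test looks for any scatter among centers. It spends its information on about 30 small units when the plausible structure is two groups. A non-significant result would be read as support for one common rate even where the two countries differ by a clinically noticeable amount. A significant result would show that centers vary without saying whether country is the reason.

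At stake is how far the pooled rate can be read as describing either country. Country is known for every subject, so a sharper question can be asked with data already held. If the country comparison is added only after the results are seen, it carries less weight than one named beforehand.

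**Working it through.** The plan's available text gives no power or detectable difference for this check, so there is no figure to reproduce.

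**Inputs from the documents**
- Test level 15%; random-center logistic model; merging below five (11.3.3).
- At least 200 PVI-only subjects, at most 400 subjects overall, about 30 sites (7.1); cap of 20 per site without sponsor approval (11.2.3).
- Average center size: 200/30 = 6.7 to 400/30 = 13.3.
- Anchor for effectiveness: about 65–70% reported for another cryoballoon (4.1).

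**Assumptions not in the documents**
- Country split 50:50 or 70:30.
- Country rates of 75 vs 65%, 80 vs 65% and 85 vs 65%.
- Gamma-distributed center recruitment; binary 12-month outcome without censoring; country as the only source of center variation.

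**Why the center test is weak.** Take 80 vs 65% with a 50:50 split.
- Logits are ln(0.80/0.20) = 1.386 and ln(0.65/0.35) = 0.619, a difference of 0.767.
- The between-center variance this creates is (0.767/2)² = 0.147.
- The sampling variance of one center's logit is about 1/(n·p·q) = 1/(6.67 × 0.725 × 0.275) = 0.75.
- The signal is therefore about one fifth of the noise per center.

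**Planned test, simulated.** Centers with fewer than five subjects were merged in random order, ignoring country. The random-intercept logistic model was fitted by Gauss-Hermite likelihood. The variance was tested by likelihood ratio at 15% against the 50:50 mixture reference (critical value 1.07), with 600 runs per case. Monte Carlo standard error is √(0.2 × 0.8/600) = 1.6 points at 20% power.

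**Direct country contrast.** Power = Φ[(|p₁−p₂| − z·SE₀)/SE₁], where SE₀ uses the pooled rate, SE₁ the separate rates, and z = 1.44 for two-sided 15%. For 80 vs 65% with 100 per country:
- SE₀ = √(2 × 0.725 × 0.275/100) = 0.0631
- SE₁ = √((0.16 + 0.2275)/100) = 0.0622
- Power = Φ[(0.15 − 1.44 × 0.0631)/0.0622] = Φ(0.95) = 83%

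**Results** (ranges over the two splits)

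| N | Rates | Planned center test, 15% | Direct contrast, 15% |
|---|---|---|---|
| 200 | 70 vs 70 | 9–10% | 15% |
| 200 | 75 vs 65 | 20% | 50–54% |
| 200 | 80 vs 65 | 28–30% | 78–83% |
| 200 | 85 vs 65 | 47–55% | 94–97% |
| 300 | 75 vs 65 | 20–21% | 62–67% |
| 300 | 80 vs 65 | 39–42% | 90–93% |
| 300 | 85 vs 65 | 69–73% | 99–100% |
| 400 | 75 vs 65 | 24–27% | 72–77% |
| 400 | 80 vs 65 | 47–54% | 95–97% |
| 400 | 85 vs 65 | 82–86% | about 100% |

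Section 11.3.3 does not name the type of variance test. With a plain one-degree-of-freedom chi-square reference, power at N = 200 falls to 9–10%, 15–18% and 34–43% for the three differences.

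For safety, with 98 vs 94% event-free assumed, the planned test flags 13–14% at N = 200 and 20–21% at N = 400. The direct contrast flags 50–51% and 70–73%.

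**Role of merging.** At N = 200 about 12 of 30 centers fell below five and formed about four supercenters, of which 2.1–2.6 mixed countries. Restricting merging to within country (80 vs 65%, 1,500 runs, three spreads of center size) gave 31–33% power, against 30–32% with cross-country merging.

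**The case against.** Several points on the other side stand.

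- **The merging rule.** A reader might infer that cross-country supercenters average the difference away. The simulation does not support that: within-country merging changes power by 0–2 points. The loss comes from the type of test.
- **The study's purpose.** A reader might infer that comparing Japan with South Korea is a stated aim. It is not. The objective in 6.1 contains no such comparison, and sections 4.1 and 4.2 mainly set the two countries together against Europe and North America. For that contrast 11.3.5 plans a propensity-adjusted comparison with the European post-market study. The remark in 7.3 speaks of enrollment regions in general.
- **Open lists.** Country is not prespecified, but it is not excluded either. No formal hypotheses are planned, and no country-specific conclusion is promised.
- **Country balance.** A reader might infer from the roof-line remark that the countries will be unevenly represented in the PVI-only set. The documents give no figure, and 7.3 says the extent of use is unknown.
- **Matching of test size.** With no difference, the center test rejects in 9–12% of runs across the sample sizes, below its nominal 15%, which flatters the direct contrast somewhat. But at a two-sided 5% level the direct contrast still detects 31–34% and 61–66% at N = 200 for 10 and 15 points, above the planned test's 20% and 28–30% at 15%.

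These points narrow the claim. They do not answer why the one stated check on pooling leaves out country.

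**Conclusion.** The point holds as a weakness of method. At 200 subjects the check in 11.3.3 would miss a pure country difference of 10 points in about 80% of trials and of 15 points in about 70–72%. A direct contrast at the same level would miss about 46–50% and 17–22%. It would be too strong to call the planned test blind to country: a 20-point difference is close to a coin flip at 200 subjects and is found in 82–86% of trials at 400. At any sample size, a positive result could not be attributed to country.

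The figures rest on assumed country splits, rates and center sizes, and on country being the only source of center variation. The N = 400 row would need nearly the whole enrollment ceiling to be PVI-only. A separate simulation with 20 and 10 centers, 200 subjects and rates of 80 vs 70% and 82 vs 67% gave 19% and 29% for the planned test and 54% and 82% for the direct contrast. The pattern therefore does not hang on one set of inputs.

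**What to change.** - **11.3.3:** add country as a fixed effect with center random within country. Judge the country term at the 15% level already in use, and report the country difference with its confidence interval.
- **11.3.2:** name Japan versus South Korea as a subgroup, and give both primary Kaplan-Meier rates with log-log intervals for each country.
- **11.3.4:** name country as a candidate covariate.
- **Secondary tidying in 11.3.3:** form supercenters within country, and count subjects in the analysis set. Under section 9.1, "Subjects who have given written informed consent are considered enrolled in the study", so a center can reach five enrollments with fewer than five analysed PVI-only subjects. Within-country merging alone would barely change power, and the effect of the counting rule has not been quantified.

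The cost is SAP wording and a few tables; no new data, visits or subjects are needed. The drawback is imprecision, most of all in the smaller country. At N = 200 with 80 vs 65%, the 95% half-width of the difference is 1.96 × 0.0622 = 12 points for a 50:50 split. For 140 and 60 subjects it is 1.96 × √(0.16/140 + 0.2275/60) = 14 points. Showing that width is more informative than a non-significant center-variance test.

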11.3.4. Multivariable Analyses

For each primary endpoint, univariate analyses of the following covariates will be performed, and any found to be significantly associated with the outcome at the 0.15 alpha level will be included as covariates in a multivariate regression model.

The analysis will be done for the entire study cohort as well as for the following treatment cohorts:

- PVI-only subjects
- PVI+ subjects
- Subjects treated with the POLARx™ FIT device

Backward selection with 0.15 alpha level stay criterion will be used to determine the final multivariate model. The list of baseline covariates includes, but is not necessarily limited to:

- Subject demographics (e.g. age, gender)
- Subject baseline characteristics (e.g. LVEF and LA diameter)
- Procedural techniques (e.g., esophageal temperature monitoring,)

Additional multivariable analyses will be performed to assess on the effect of cryo dosing parameters on acute (e.g. procedure duration, dwell time, acute success, acute adverse events, and other procedural outcomes) and chronic parameters e.g. (freedom from effectiveness failure). Analyses will be performed on a per-subject and per-vein basis. Cryo dosing parameters to be assessed for use in the per-subject model may include, but not be limited to:

- Total number of applications > 60s
- Total application duration.

Cryo dosing parameters to be assessed for use in the per -vein model may include, but not be limited to:

- Total number of applications > 60s
- Total application duration.
- Occlusion score
- TTI driven applications (yes or no)
- TTI.

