10.5.2. Cryoablation procedure steps

Preparation activities should be performed as follows:

1. Assessment of presenting rhythm by 12-lead ECG.
2. Baseline the fluoroscopy exposure time (Time 0).
3. Place additional diagnostic catheters, for example in the coronary sinus or for pacing the phrenic nerve, at the discretion of the physician.
4. Per institutional protocol, complete transseptal access (single or double).
5. Prepare the Cryo Steerable Sheath. Insert the sheath over the guidewire and advance the sheath across the atrial septum.
6. Prepare the Cryoablation Catheter and the Cryo Mapping Catheter. Insert the Cryo Mapping Catheter into the Cryoablation Catheter. Insert the Cryoablation Catheter into the Cryo Steerable sheath and advance it into the left atrium.

7. Baseline the LA dwell time.

Following the step-wise approach for the ablation procedure is recommended:

8. Navigating and positioning of the balloon

- a. Advance the Cryo Mapping Catheter and Cryoablation Catheter under fluoroscopic guidance to the proximity of the target PV
- b. Inflate the balloon while remaining outside of the target PV
- c. Occlude targeted vein by advancing the balloon as necessary but remain outside of the tubular portion of the vein.
- d. Verify balloon position of the PV occlusion. Verification may be performed with fluoroscopy and/or contrast injection or other technique (per investigator's discretion).
- e. If the selected vessel is a right PV, start phrenic nerve pacing prior to starting the cryoablation.

9. Cryo Ablation of all target PVs

- a. Perform cryo ablation. A minimum ablation time of TTI + 120sec is highly recommended, where possible. If no PV potential is visible, a minimum ablation time of 180sec is highly recommended.
- b. During each ablation application: annotate the anatomical location of ablation, the time-to-isolation* (as observed on the PolarMap EGMs and representing the time point when electrical activity disappears) and the ablation duration.

* TTI is required to be captured through the console, when available.

- c. Wait for the thawing phase to be completed prior to manipulating the Cryoablation Catheter.
- d. As needed, perform additional cryoablation in the same PV, adjusting the position of the Cryoablation Catheter, if necessary.

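### Section 11.3.4 lists time-to-isolation (TTI) covariates for per-vein models without keeping them out of models of acute success, where an association would be largely built in

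*Combined protocol and SAP*

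**What the plan says.** Section 11.3.4 commits to additional multivariable analyses of the effect of cryo dosing parameters. The acute outcomes are "acute (e.g. procedure duration, dwell time, acute success, acute adverse events, and other procedural outcomes"); freedom from effectiveness failure is the chronic example. On the unit of analysis it says: "Analyses will be performed on a per-subject and per-vein basis".

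The per-vein covariates are introduced as candidates: "Cryo dosing parameters to be assessed for use in the per -vein model may include, but not be limited to". The list holds the number and total duration of applications, an occlusion score, "TTI driven applications (yes or no") and TTI itself. The two TTI items appear only in the per-vein list.

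Section 10.5.2 describes TTI as read from the mapping-catheter electrograms, "representing the time point when electrical activity disappears". Recording is conditional: "TTI is required to be captured through the console, when available". Two application-time recommendations follow from whether a potential can be seen. The first is tied to TTI: "A minimum ablation time of TTI + 120sec is highly recommended, where possible". The second covers veins in which the electrograms show nothing to time from: "If no PV potential is visible, a minimum ablation time of 180sec is highly recommended".

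Section 10.5.4 collects TTI for each application, if available, and isolation success for each vein by entrance block. Section 6.2.2 judges acute procedural success at the end of the index procedure, for all veins together.

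The plan does not define a TTI-driven application, does not say how a missing TTI is handled, and does not say how several applications to one vein are reduced to one covariate value.

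**The concern.** A covariate in a model of acute success should be able to take its values whether or not the vein ends up isolated. TTI cannot: a value requires that isolation was observed during the freeze. TTI-driven status appears to share the property, because an application timed from TTI needs a TTI to time from.

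If either is entered in a per-vein model of acute success, two things follow. With the yes/no covariate, failed veins collect in the "no" group whatever the effect of dosing. With continuous TTI, veins without a value drop out of a complete-case fit, and they include most or all of the failures.

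The stated purpose of these models is to assess the effect of dosing parameters, so a built-in association would be laid out as if it were a dosing effect.

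**Working it through.** The plan gives no power, effect size or event count for these models, so there is no figure to reproduce. The check has a logical part and an illustration.

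**Logic.**
- TTI recorded → electrical activity was seen to disappear → the vein was isolated at that moment (10.5.2).
- TTI not recorded → either no isolation was seen, or no potential was visible. A vein of the second kind can still pass the entrance-block test.
- Success is judged later than TTI, so a vein may isolate, yield a TTI, reconnect and finish as a failure.

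The dependence is therefore strong but one-way, and reconnection weakens it.

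**Inputs.** The minimum of 200 PVI-only subjects is from section 7.1. The rest are assumptions:
- four veins per subject, so N = 200 × 4 = 800 veins;
- per-vein success p = 95%, 98% or 99%;
- share of veins with a visible potential v = 50% or 80%, unrelated to success (no true effect);
- share of failed veins that isolated transiently ρ = 0, 10% or 25%, with TTI recorded if the potential was visible.

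**Expected cells.**
- success, TTI recorded: a = N·p·v
- success, no TTI: b = N·p·(1 − v)
- failure, TTI recorded: c = N·(1 − p)·ρ·v
- failure, no TTI: d = N·(1 − p)·(1 − ρv)

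Odds ratio = ad/(bc) = (1 − ρv) / [ρ(1 − v)]. N and p cancel, so the false odds ratio does not depend on the failure rate.

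Example: p = 98%, v = 50%, ρ = 10% gives a = 392, b = 392, c = 0.8, d = 15.2, and 392 × 15.2 / (392 × 0.8) = 19.

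| ρ | v = 50% | v = 80% | failures left in a complete-case TTI model |
|---|---|---|---|
| 0 | unbounded | unbounded | 0 of 8 to 40 |
| 10% | 0.95/0.05 = 19 | 0.92/0.02 = 46 | 0.4 to 3.2 |
| 25% | 0.875/0.125 = 7 | 0.80/0.05 = 16 | 1.0 to 8.0 |

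The last column is c. It runs from p = 99%, v = 50% (8 failures in all) to p = 95%, v = 80% (40 failures). The share of failures kept is ρv, so at most 0.25 × 0.8 = 20%.

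Among veins without a TTI, success b/(b + d) is still 79% to 98% over the grid.

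The odds ratio returns to 1 only at ρ = 1, where the formula gives (1 − v)/(1 − v): every failed vein would have to have isolated first and then reconnected.

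**Significance depends on the number of failures.** Assume TTI recorded in 60% of veins (480 of 800) and no reconnection:
- 3% failures: 0/480 against 24/320, Fisher p = 1.6 × 10⁻¹⁰.
- 1% failures: 0/480 against 8/320, p = 6.2 × 10⁻⁴.
- 2 failures: 0/480 against 2/320, p = (320 × 319)/(800 × 799) = 0.16.

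The last case matters because the only acute success rate in the documents is above 99% (section 4.1, another cryoballoon system, unit not stated). If that is per subject, 200 subjects give about 200 × 0.01 = 2 failures at most. These tests also treat veins within a subject as independent.

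**The case against.** The strongest reply is that the plan does not commit to the model criticised. The covariates are candidates, the outcomes are examples, and TTI is a usable covariate for several of them, such as procedure duration or later freedom from failure. That is correct, and the point is confined accordingly. What remains is that the analyses will be done, acute success is named, and no sentence prevents the pairing.

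Three stronger readings are tempting, and the documents do not support them.
- A reader might infer that TTI status simply encodes the outcome. It does not: a missing TTI also arises when no potential is visible, and isolation during a freeze is not isolation at the end of the procedure.
- A reader might take it as stated that a TTI-driven application requires observed isolation. The term is undefined; the dependence is inferred from the TTI-based application time in 10.5.2.
- A reader might expect an infinite odds ratio with a very small p-value. That needs zero reconnection and enough failures, both assumed. With two failed veins p is 0.16.

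It is also fair that very few failures would make any acute-success model hard to estimate, and that an empty cell is easy to see. But a few reconnections fill the cell and leave a finite odds ratio of the size tabulated, which looks like an ordinary result. Nothing in the documents says that such a result would be used to support a dosing strategy.

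**Conclusion.** The concern holds in limited form. Section 11.3.4 permits a per-vein model of acute success with covariates whose availability depends on isolation having been observed. The association would be largely built in: unbounded without reconnection, and about 7 to 46 on the odds-ratio scale if 10% to 25% of failed veins had isolated transiently. A complete-case model on continuous TTI would drop 80% to 100% of failures on the same assumptions. Visibility, reconnection and the number of veins are not given in the documents, and statistical significance depends on how many veins fail.

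For chronic outcomes the problem is different: TTI is selectively available, not circular. The primary Kaplan-Meier estimates and the secondary endpoints are untouched, since this is an exploratory analysis without formal hypotheses. It is worth correcting because the bias is structural and the correction is cheap.

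**What to change.** In section 11.3.4, state that TTI and TTI-driven status will not be covariates in models of acute success. State also that continuous TTI will be used only for other or later outcomes, among veins with a recorded TTI, with the number of excluded veins shown. In the same place, define a TTI-driven application and say how several applications to one vein are summarised.

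This is a wording change with no new data, and section 11.3.6 provides for changes documented before the analyses are run.

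Two refinements are optional: a factor that separates veins with no visible potential from veins with a visible potential that did not isolate, or TTI analysed as an outcome censored at the end of the freeze. Both need a record of whether a potential was visible. Section 10.5.4 does not list that item, although its list is not exhaustive, so these should be proposed only after checking the case report form.
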